### 3.5 Data collected in the CRF

A case report form (CRF) has to be filled in by all the GPs for each patient included to define patient's characteristics, current pain, personal history of cardiovascular disease and risk factors. It will also provide investigators with information regarding complementary investigations, referrals or hospitalizations for each patient at the time of index visit.

GPs of the intervention group will be asked to calculate the risk of cardiogenic chest pain for each patient with the CPR. The CRF also includes questions directly addressed to GPs to appreciate use, satisfaction and acceptability of the CPR.

GPs who belong to the usual care group will have to evaluate the risk of cardiogenic chest pain according to their clinical judgement only.

As all the items of the CPR are part of usual practice (patient's history and physical examination) investigators will be able to calculate patients' risk of cardiogenic chest pain a posteriori in the usual care group with the data collected in the CRF.

[figure not shown]
(See Annex 2 for complete CRF)

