### 4.1 Inclusion criteria

Adults (aged 18 years and over) reporting any type of chest pain (defined as a superficial or deep pain in the area indicated in **Figure B** (page 12), with or without posterior irradiation and/or irradiation in arms) will be asked to enter the study. Subjects will be enrolled even if chest pain is not the main complaint, if it is revealed by systematic anamnesis or if there is yet a known history of chest pain or cardiovascular disease. Telephonic interviews, emergency consultations and home visits will also be included.

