## 5. Study CPR

GPs selected to use the cardiovascular CPR as an assistive tool will have to calculate the risk of cardiac origin to chest pain for each patient. According to Gencer and al. (8), the Swiss CPR is the following:

Swiss Heart Score	
Men over 55 years, women over 65 years	2 points
Known cardiovascular risk	2 points
Personal history of cardiovascular disease	2 points
Substernal pain	2 points
Duration of pain from 1 to 60 minutes	1 point
Increasing with effort	1 point
No tenderness at palpation	1 point
Total < 5 points: low risk of cardiogenic chest pain	
Total 5 to 7 points: intermediate risk of cardiogenic chest pain	
Total > 7 points: high risk of cardiogenic chest pain	
- Sensitivity 97.6%, specificity 71.3%, negative likelihood ratio 0.033, negative predictive value 99.5% (derivation cohort)	
- Sensitivity 85.6%, specificity 47.2%, negative likelihood ratio 0.305, negative predictive value 94.8% (validation cohort)	

Except filling in the CRF and – for GPs allocated to the intervention group - calculating the risk of cardiogenic chest pain, taking history of the patient, examination, and further investigations have to be done as usual by GPs, according to their scientific knowledge and clinical experience.

Intensive training will provide GPs of the intervention group all information concerning aim, performance and limitations of the cardiovascular CPR as an assistive, prognostic tool (see Annex 1). Diagnosis and treatments should not be altered.

N.B. Investigators may choose to use the Marburg Heart Score instead of the Swiss Heart Score according to the not yet published results of Marburg's last external validation study. This will be decided before submission of the current protocol to the ethical committee.

Marburg Heart Score	
Men over 55 years, women over 65 years	1 point
Known clinical vascular disease*	1 point
Pain worse during exercise	1 point
Pain not reproducible by palpation	1 point
Patient assumes pain is of cardiac origin	1 point
Total ≤ 2 points: low risk of cardiogenic chest pain	
* Coronary artery disease, occlusive vascular disease or cerebrovascular disease	
Sensitivity 89.1%, specificity 63.5%, negative likelihood ratio 0.17, negative predictive value 97.9% (results to be published)	

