## 10.2 Data analysis

- a) Sampling and characteristics of GPs recruited (+/- Baseline Survey)
- b) Patients characteristics in usual practice group versus CPR group (age, sex, personal history of cardiovascular disease, cardiovascular risk factors, emergency consultation, telephonic interview, home visit, chest pain as main or secondary complaint)
- c) Patients characteristics within CPR group: low-risk versus high-risk of cardiogenic chest pain

- d) Impact of the CPR within CPR group

	CPR < 5 points (low risk)	CPR 5 to 7 points (intermediate risk)	CPR > 7 points (high risk)
Extra investigations			
Referral			
Patient's outcome			

- e) CPR calculated *a posteriori* in usual practice group, endpoints values and comparison of endpoints in low risk patients of usual practice group versus CPR group
- f) CPR group versus usual practice group

	CPR	Usual practice
Extra investigations		
Referral		
Patient's outcome		

- g) Implementation: use/non use rate of the CPR, acceptability and satisfaction.

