### **11.3 Information and consent**

Each patient eligible for the study will be asked to participate at index visit. Patients agreeing to participate will get an information form to explain the purpose of the study and the modalities of follow up (see Annex 4, in French). They will be asked to sign a consent form and will be informed of their right to withdraw at any time of the study.

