### Douleur thoracique:

**Contexte :** nouvelle  / connue  plainte principale  / plainte secondaire

**Intensité:** faible  modérée  forte

[figure not shown]
**Installation:** soudaine  progressive

**Evolution:** en augmentation  en diminution  intermittente   
constante avec exacerbations

**Durée:** <1 minute  <15 minutes  <1 heure  heures   
jours  mal défini

**Type:** superficielle  profonde  oppressante  en lancées   
brûlure

**Localisation :** rétrosternale  transfixiante  localisée  étendue

Préciser (avec irradiation si présente) :

**Facteur déclenchant:** effort  mouvement  décubitus  repas   
anxiété  palpation

**Facteur aggravant:** toux  respiration  position  déglutition   
effort

Autre(s) caractéristique(s) (préciser) : \_\_\_\_\_

**Symptômes d'accompagnement :****Général :** fièvre  frissons  sudations  altération conscience **Cardiovasculaire :** palpitation  syncope  tachycardie  arythmie   
instabilité hémodynamique   
autre  (préciser) : \_\_\_\_\_**Respiratoire :** dyspnée  toux  expectorations   
autre  (préciser) : \_\_\_\_\_**Digestif :** dysphagie  reflux  épigastralgies   
autre  (préciser) : \_\_\_\_\_**Articulaire :** préciser si présent(s) : \_\_\_\_\_**Facteurs de risque :**HTA  diabète  dyslipidémie Tabagisme  : \_\_\_\_ UPA OH  : \_\_\_\_ dl/semaineAnamnèse familiale positive Antécédents personnels cardiovasculaires (maladie coronarienne, maladie cérébrovasculaire, artériopathie périphérique) Antécédent personnel maladie thromboembolique veineuse **Score clinique cardiovasculaire (uniquement pour les médecins du « groupe CPR ») :**

Swiss Heart Score	
Men over 55 years, women over 65 years	2 points
Known cardiovascular risk	2 points
Personal history of cardiovascular disease	2 points
Substernal pain	2 points
Duration of pain from 1 to 60 minutes	1 point
Increasing with effort	1 point
No tenderness at palpation	1 point
Total < 5 points: low risk of cardiogenic chest pain	
Total 5 to 7 points: intermediate risk of cardiogenic chest pain	
Total > 7 points: high risk of cardiogenic chest pai	
- Sensitivity 97.6%, specificity 71.3%, negative likelihood ratio 0.033, negative predictive value 99,5% (derivation cohort)	
- Sensitivity 85.6%, specificity 47.2%, negative likelihood ratio 0.305, negative predictive value 94.8% (validation cohort)	

**Total :** \_\_\_\_ points

Alternativement :

Marburg Heart Score	
Men over 55 years, women over 65 years	1 point
Known clinical vascular disease*	1 point

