Pain worse during exercise	1 point
Pain not reproducible by palpation	1 point
Patient assumes pain is of cardiac origin	1 point
Total ≤ 2 points: low risk of cardiogenic chest pain	
* Coronary artery disease, occlusive vascular disease or cerebrovascular disease	
Sensitivity 89.1%, specificity 63.5%, negative likelihood ratio 0.17, negative predictive value 97.9% (results to be published)	

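### The case report form does not reliably record palpation in both arms (nor, for the Marburg score, the patient's belief at all), so low-risk status may be ascertained differently by arm in comparison 10.2(e)

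*Protocol*

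**What the plan says.** Section 3.5 gives as its reason "As all the items of the CPR are part of usual practice" and concludes that the research team can "calculate patients' risk of cardiogenic chest pain a posteriori in the usual care group with the data collected in the CRF". Section 10.2, item (e), rests on this: it plans a "comparison of endpoints in low risk patients of usual practice group versus CPR group". Item (e) mentions scoring after the fact for the usual-practice group only. Sections 3.5 and 5 have the CPR-group GPs calculate the score themselves.

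The Swiss score (section 5) gives one point for "No tenderness at palpation", and a total below 5 is low risk. Section 5 also leaves open a switch to the Marburg score, where 2 points or fewer out of 5 is low risk and one item is "Patient assumes pain is of cardiac origin".

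Annex 2 contains the CRF. Its score box is reserved for the CPR group. In the part that both arms complete, palpation is one tick option under "Facteur déclenchant", beside effort, movement, lying down, meals and anxiety. Section 4.1 also admits contacts at which nobody can palpate the chest, namely those by telephone: "Telephonic interviews, emergency consultations and home visits will also be included".

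**The concern.** An item can be routine without being written down, and only what is written down can be scored later. Palpation is the one Swiss item whose point is earned by a negative finding. For the other tick-box items a blank adds nothing. For palpation, a blank read as no tenderness adds a point, although it may also mean that the chest was not palpated, or that tenderness was found but not regarded as a trigger of the pain. The score box reminds CPR-group GPs of this item; nothing in the common fields reminds control GPs.

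Item (e) looks at the patients in whom the rule is meant to spare investigations. If the low-risk group is formed by prompted GPs in one arm and rebuilt from an ambiguous box in the other, part of a difference in tests, referrals or outcome (or part of an absent difference) could reflect who was placed in the stratum.

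Section 10.3 does not repair this. Its sequence of contacting, extrapolating and excluding starts only when a value is recognised as missing, and an unticked box does not look missing. A later analysis plan can fix an algorithm, but it cannot recover an observation that was never collected.

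**Working it through.** The protocol states no figure on this point, so there is none to reproduce. The check maps score items to CRF fields and then counts where the doubtful item matters.

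**1. Items against the fields common to both arms (Annex 2)**

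| Swiss item | Points | Common field |
|---|---|---|
| Age and sex | 2 | age, sex |
| Cardiovascular risk | 2 | risk-factor boxes |
| Cardiovascular history | 2 | personal history box |
| Substernal site | 2 | retrosternal box |
| Duration 1 to 60 minutes | 1 | duration boxes |
| Worse with effort | 1 | effort box |
| No tenderness | 1 | palpation as a trigger only |

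Six of seven items are recorded and the seventh has an imperfect proxy. Of the five Marburg items, patient belief has no common field, and the Marburg palpation item has the same weak proxy.

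**2. When palpation decides the Swiss low-risk class.** The cut-off is below 5, so palpation matters only if the other six items (weights 2, 2, 2, 2, 1, 1) total exactly 4.
- Total 4: two 2-point items and no 1-point item, C(4,2) = 6; or one 2-point item and both 1-point items, 4. Together 10.
- Total 3 or less (always low): no 2-point item, 4 patterns; one 2-point item with at most one 1-point item, 4 × 3 = 12. Together 16.
- Total 5 or more (never low): 64 − 10 − 16 = 38.

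Palpation is decisive in 10 of 64 patterns; the class is fixed without it in the other 54.

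**3. When belief decides the Marburg low-risk class.** This happens when the other four items total exactly 2: C(4,2) = 6 of 16 patterns, taking palpation as known.

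**4. Illustration of size (Swiss).** Every input here is an assumption; the protocol gives none. The items are independent with a common frequency p of 0.2 to 0.5. A share t of patients, 40% to 60%, is tender. A fraction f of tender controls, 10% to 50%, is left unticked and scored as not tender. The CPR arm is classified correctly. Tests are run in 30% of patients whose other items total 3 or less and in 45% of those at 4, with no effect of the rule.

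Let A be the share with other items at 3 or less, and B the share at exactly 4.
- Low-risk share, CPR arm: A + B·t
- Low-risk share, control arm: A + B·t·(1 − f)

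Example with p = 0.4, t = 0.6, f = 0.5:
- B = 6(0.4²)(0.6⁴) + 4(0.4)(0.6³)(0.4²) = 0.124 + 0.055 ≈ 0.180
- A = 0.6⁴ + 4(0.4)(0.6³)(1 − 0.4²) = 0.130 + 0.290 = 0.420
- CPR-arm share: 0.420 + 0.108 = 0.528
- Control-arm share: 0.420 + 0.054 = 0.474, which is 5.4 points lower
- Tests, CPR arm: (0.420 × 0.30 + 0.108 × 0.45)/0.528 = 0.331
- Tests, control arm: (0.420 × 0.30 + 0.054 × 0.45)/0.474 = 0.317
- Spurious difference: about +1.4 points, against the rule

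Over the whole grid, B is 11.5% to 18%, the control low-risk share is understated by about 0.5 to 5.4 points, and the spurious difference in tests is about +0.1 to +1.7 points. For Marburg, the share at the decisive total is 6p²(1 − p)², or 15% to 38%.

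**5. Direction.** It depends on how gaps are scored. Reading a Swiss blank as not tender takes tender controls out of the low-risk group. Reading it as tender would bring non-tender controls in. Scoring the absent Marburg item as 0 also brings controls in.

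**The case against.** The strongest reply is that item (e) never says that the GP's own total defines low risk in the CPR arm. Both arms complete the common fields, so one algorithm could serve both, and choosing it is ordinary work for an analysis plan. That is fair as far as it goes. But one algorithm applied to the present fields would still meet an ambiguous palpation box, completed by prompted GPs in one arm and unprompted GPs in the other, and it could not supply the Marburg item.

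A reader might also infer more than the documents support:
- *That the control score cannot be computed.* For the Swiss score, six items are recorded and palpation is seldom decisive. For Marburg, which is only an option, the class is fixed in 10 of 16 patterns even without belief.
- *That the comparison is biased in a known direction.* Neither the size nor the direction is shown.
- *That the 43% share of chest wall syndrome (section 1.1) measures the problem.* It is a diagnosis share, neither the share with tenderness nor the share at the decisive total. Likewise, at 12% prevalence the low-risk stratum is 0.472 × 0.88 + 0.144 × 0.12 = 43.3% of patients on the validation figures, or 0.713 × 0.88 + 0.024 × 0.12 = 63.0% on the derivation figures. That is the size of the stratum, not of the error.
- *That telephone contacts create the imbalance or should be ineligible.* They enter both arms, so they do not by themselves separate them. Annex 2 records them and 10.2(b) tabulates them, so they can be handled in the analysis.
- *That written consent (section 11.3) is part of this problem.* That section does not fix when the form is signed, and it has no bearing on whether the score can be computed.

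**Conclusion.** The point holds in a limited form. The statement in section 3.5 goes further than the CRF allows: absent tenderness is not reliably recorded in the fields common to both arms, and patient belief is not recorded there at all. Low-risk status may therefore be ascertained differently by arm, and comparison 10.2(e) may be biased by an amount that the documents do not determine. With the Swiss score, only patients whose other six items total exactly 4 can be misplaced through palpation. On the assumed inputs above, the resulting error in the difference in tests is under 2 percentage points. The Marburg gap is conditional on that score being chosen.

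The whole-arm comparison 10.2(f) does not use the score, and the sample size rests on paraclinical tests over whole arms, so neither is touched. The conclusion assumes that the figure in the pain section of Annex 2, which could not be read in the text reviewed, holds no examination field; nothing around it suggests one.

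**What to change.** - **Annex 2, section completed by both arms:** add tenderness at palpation with three answers (yes, no, not examined). While the Marburg score remains possible, add whether the patient thinks the pain is cardiac (yes, no).
- **Sections 3.5 and 10.2(e):** state that the low-risk stratum is derived centrally, by one algorithm, from the common items in both arms. Keep the GP's own total for the implementation endpoints.
- **Contacts without examination, such as telephone contacts:** state one rule for both arms, for example excluding them from (e) or running a sensitivity analysis. Section 4.1 need not change.

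The cost is two CRF lines and a few sentences. There is a small risk that the added items cue control GPs, whom section 3.1 wants unaware of the rule. The change has to be made before the forms are in use, because the missing observations cannot be reliably recovered afterwards.

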## 4. Study population

Target population are inhabitants of Switzerland who consult primary care settings.

### 4.1 Inclusion criteria

Adults (aged 18 years and over) reporting any type of chest pain (defined as a superficial or deep pain in the area indicated in **Figure B** (page 12), with or without posterior irradiation and/or irradiation in arms) will be asked to enter the study. Subjects will be enrolled even if chest pain is not the main complaint, if it is revealed by systematic anamnesis or if there is yet a known history of chest pain or cardiovascular disease. Telephonic interviews, emergency consultations and home visits will also be included.

#### 4.2 Exclusion criteria

Patients unable to communicate with physicians (language barriers), patients for whom follow-up may not be feasible, obvious traumatic or extrathoracic origin to chest pain, severe psychiatric comorbidities, refusal or impossibility to consent will be excluded from the current study.

#### 4.3 Withdrawal criteria

As the only intervention in this study is to calculate a risk thanks to a CPR and to collect information regarding patient's characteristics and use of the CPR, no withdrawal criteria are established. Patients are free to drop out the trial at any time and just need to inform their physician so that no new information is communicated to the data centre.

In case of patient's withdrawal no replacement procedure is planned. A complete analysis of patient's characteristics will be performed in order to avoid any bias induced by the loss of patients.

#### 4.4 Selection and recruitment procedure

Swiss GPs and physicians of the Department of Ambulatory Care and Community Medicine in Lausanne will be contacted and asked to participate the study. Starting from a defined date, each GP will enrol a defined number of patients reporting any type of chest pain, according to inclusion criteria.

Sampling of all the GPs recruited will be performed in order to assess characteristics of participants (age, place, type of practice) and minimize cohort effect. Investigators may decide to use pre-existing GPs network such as Sentinella, which can insure correct sampling of Swiss GPs.

## 5. Study CPR

GPs selected to use the cardiovascular CPR as an assistive tool will have to calculate the risk of cardiac origin to chest pain for each patient. According to Gencer and al. (8), the Swiss CPR is the following:

Swiss Heart Score	
Men over 55 years, women over 65 years	2 points
Known cardiovascular risk	2 points
Personal history of cardiovascular disease	2 points
Substernal pain	2 points
Duration of pain from 1 to 60 minutes	1 point
Increasing with effort	1 point
No tenderness at palpation	1 point
Total < 5 points: low risk of cardiogenic chest pain	
Total 5 to 7 points: intermediate risk of cardiogenic chest pain	
Total > 7 points: high risk of cardiogenic chest pain	
- Sensitivity 97.6%, specificity 71.3%, negative likelihood ratio 0.033, negative predictive value 99.5% (derivation cohort)	
- Sensitivity 85.6%, specificity 47.2%, negative likelihood ratio 0.305, negative predictive value 94.8% (validation cohort)	

Except filling in the CRF and – for GPs allocated to the intervention group - calculating the risk of cardiogenic chest pain, taking history of the patient, examination, and further investigations have to be done as usual by GPs, according to their scientific knowledge and clinical experience.

Intensive training will provide GPs of the intervention group all information concerning aim, performance and limitations of the cardiovascular CPR as an assistive, prognostic tool (see Annex 1). Diagnosis and treatments should not be altered.

N.B. Investigators may choose to use the Marburg Heart Score instead of the Swiss Heart Score according to the not yet published results of Marburg's last external validation study. This will be decided before submission of the current protocol to the ethical committee.

Marburg Heart Score	
Men over 55 years, women over 65 years	1 point
Known clinical vascular disease*	1 point
Pain worse during exercise	1 point
Pain not reproducible by palpation	1 point
Patient assumes pain is of cardiac origin	1 point
Total ≤ 2 points: low risk of cardiogenic chest pain	
* Coronary artery disease, occlusive vascular disease or cerebrovascular disease	
Sensitivity 89.1%, specificity 63.5%, negative likelihood ratio 0.17, negative predictive value 97.9% (results to be published)	

## 6. Evaluation criteria

Aiming to assess both implementation of the cardiovascular CPR and its potential effect on chest pain management, evaluation criteria are split in two classes. On one hand, criteria concerning use of the CPR, evaluated by few questions in de CRF directly addressed to GPs. On the other hand, criteria aiming to measure impact of the CPR on chest pain management and patient's outcome. These are to be filled in by GPs for each patient complaining of chest pain at the time of the index visit (CRF) and at the end of follow-up (6 to 9 months), and by research team for intermediate analysis.

Implementation:	
Acceptability of the CPR	
 
- Use/non use of the CPR
 
- Reassurance with low-risk result
 

Satisfaction	
 
- Discrete visual analogue scale
 

Impact:	
Extra investigations of chest pain	
 
- None
 
- ECG
 
- Thoracic radiography
 
- Laboratory (CRP, FSC, CK, D-dimers, Troponines, BNP)
 
- Cardiac stress test
 
- Others (precise)
 

Referral	
 
- None
 
- Hospital / emergency setting
 
- Cardiologist (less than 6 hours, less than one week, more than one week, telephonic interview)
 
- New consultation
 
- Other (precise)
 

Patient's outcome at 9 months	
 
- Hospitalisation(s) during follow-up
 
- CHD / no CHD, with degree of certainty (discrete visual analogue scale)
 

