## 1. Background

### 1.1 Fundamentals

Chest pain is a common complaint in primary care patients (1 to 3% of all consultations) (1) and its aetiology can be miscellaneous, from harmless to potentially life threatening conditions. In primary care practice, the most prevalent aetiologies are: chest wall syndrome (43%), coronary heart disease (12%) and anxiety (7%) (2). In up to 20% of cases, potentially serious conditions as cardiac, respiratory or neoplastic diseases underlie chest pain. In this context, a large number of laboratory tests are run (42%) and over 16% of patients are referred to a specialist or hospitalized (2).

A cardiovascular origin to chest pain can threaten patient's life and investigations run to exclude a serious condition can be expensive and involve a large number of exams or referral to specialist - often without real clinical need. In emergency settings, up to 80% of chest pains in patients are due to cardiovascular events (3) and scoring methods have been developed to identify conditions such as coronary heart disease (CHD) quickly and efficiently (4-6). In primary care, a cardiovascular origin is present in only about 12% of patients with chest pain (2) and general practitioners (GPs) need to exclude as safely as possible a potential serious condition underlying chest pain. A simple clinical prediction rule (CPR) like those available in emergency settings may therefore help GPs and spare time and extra investigations in ruling out CHD in primary care patients. Such a tool may also help GPs reassure patients with more common origin to chest pain.

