### **Hospitalisations en lien avec la douleur thoracique durant la période de suivi :**

oui  / non

*Si oui*, durée : \_\_\_\_ jour(s)

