### **Diagnostic retenu pour la douleur thoracique :**

Maladie coronarienne : oui  / non

Degré de certitude : faible 0 - 1 - 2 - 3 - 4 fort

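### No index or follow-up field identifies a serious non-coronary cause of chest pain, yet tests aimed at such causes count towards the reduction the trial seeks

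*Protocol*

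**What the plan says.** Section 1.1 gives the range of disease: "In up to 20% of cases, potentially serious conditions as cardiac, respiratory or neoplastic diseases underlie chest pain". The same section puts CHD at 12%, and shortly afterwards uses that figure under a wider label: "In primary care, a cardiovascular origin is present in only about 12% of patients with chest pain".

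Section 2 (second objective) sets out to show that the clinical prediction rule (CPR) spares needless investigations without harm to patients' care or outcome. Section 10.1 sizes the trial on a difference in paraclinical tests. Among the investigations counted, section 6 lists ECG, chest radiography, stress test and "Laboratory (CRP, FSC, CK, D-dimers, Troponines, BNP").

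The outcome row of section 6 has two entries: "Hospitalisation(s) during follow-up" and "CHD / no CHD, with degree of certainty (discrete visual analogue scale").

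The forms follow this. In Annex 2 (index visit) the diagnostic impression is suspected coronary disease yes or no, with a certainty score. In Annex 3 (3 and 9 months) the item "Diagnostic retenu pour la douleur thoracique" offers only coronary disease yes or no, with the same certainty score. The item "Hospitalisations en lien avec la douleur thoracique durant la période de suivi" is answered yes or no, with a number of days.

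**The concern.** The score speaks only to coronary disease, but the benefit side of the trial takes in tests that look for other things. Chest radiography, D-dimers, CRP and blood count serve largely to find the respiratory, thromboembolic, infective or neoplastic causes that a low coronary score says nothing about. Annex 1 tells GPs in the CPR group to decide on further tests after calculating the score, and section 6 makes reassurance from a low score a measured outcome.

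If a reassured GP omits such a test and a serious non-coronary disease emerges later, the spared test counts towards the reduction sought and the diagnosis is entered as no CHD. The safety half of the second objective would then rest on data that cannot name the event. The 3-month look for unfavourable effects (sections 3.4 and 8.2) uses the same form and has the same gap.

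**Working it through.** **1. The plan's own figures.** 2 arms × 150 GPs × 50 patients = 15,000 (section 10.1), which reproduces. The control rate for paraclinical tests, 284/672 = 42.3%, agrees with the stated 42%.

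**2. Size of the group without a diagnosis field.** The protocol does not state this share; it follows by subtraction from section 1.1, assuming that all CHD lies within the serious 20%.

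- Serious causes, all kinds: up to 20%. CHD: 12%.
- Serious non-coronary share: 20% − 12% = up to 8%.
- Patients: 0.08 × 15,000 = up to 1,200, or 600 per arm.
- Share of the serious causes: 8/20 = up to 40%.
- Share of patients coded no CHD: 8/88 = up to 9.1%.

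The 20% is an upper bound. If the true serious share were 16% or 14% (assumed values), the count would be 0.04 × 15,000 = 600 or 0.02 × 15,000 = 300.

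Because section 1.1 attaches 12% both to CHD and to cardiovascular origin, it is unclear whether other cardiac disease falls inside the remaining 8%. This affects what the remainder contains, not the subtraction.

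**3. What each field would show for a patient whose serious non-coronary disease is found late.**

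| Field | Content | Names the disease? |
|---|---|---|
| Annex 2, diagnostic impression | coronary disease suspected, yes/no, certainty | no |
| Annex 3, later consultations | yes/no, number | no |
| Annex 3, later investigations | type and number, no result | no |
| Annex 3, specialist referral | cardiologist or named specialty, number of visits | no |
| Annex 3, hospitalisation | yes/no, days, only if linked to the chest pain | no |
| Annex 3, retained diagnosis | coronary disease yes/no, certainty | no |

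**4. The independent review.** Section 9.1 has two physicians review a random 20% of cases: 0.20 × 15,000 = 3,000, of whom up to 0.08 × 3,000 = 240 would have a serious non-coronary cause. Section 10.2 lists no comparison of the review findings by arm.

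**5. What cannot be computed.** The documents give no rate of missed or delayed non-coronary diagnoses, with or without the score. The figures in step 2 include patients correctly diagnosed at the index visit and are not estimates of harm.

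**The case against.** The best reply is that follow-up is broader than the diagnosis field. Hospitalisation stands in the same outcome row of section 6, and Annex 3 also records repeat visits, later tests and other specialists. Under randomisation, an excess of missed disease in the CPR arm could appear as an excess of these events in the comparison of section 10.2(f). The independent physicians check diagnosis and management in a fifth of cases. Tests are listed by type, so fewer radiographs can be told from fewer stress tests. GPs are told to investigate as usual, and to go on investigating when score and clinical impression conflict.

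Much of this stands. A reader might infer that the trial sees only coronary disease and would be wholly blind to other harm; the documents do not support that, because such cases can surface indirectly.

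The indirect routes do not close the gap, however. Section 10.1 expects hospitalisations to fall under the CPR, so fewer avoidable admissions could offset added admissions for missed disease, and without a cause the two cannot be separated. Annex 3 asks only about admissions linked to the chest pain. Referral and test fields carry no result. The review is quality control in a sample, and section 3.1 directs its check of the initial diagnosis to cardiogenic pain.

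**Conclusion.** The point holds as a gap in data collection. The only diagnosis the forms can record is CHD or not, so a serious non-coronary cause is coded like a benign one and can be inferred only from events that carry no diagnosis. Up to about 8% of patients, at most some 1,200 of 15,000, may have such a cause. This rests on the two figures in section 1.1, on reading 20% as a ceiling, and on all CHD lying within it.

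Two stronger readings should be avoided. The 8% is not the protocol's own estimate. And 1,200 is not the number that would be missed: it is a ceiling on everyone with such a cause, most of whom might be recognised at once.

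Within those limits, the claim of no harm in the second objective cannot be properly supported for diseases that section 1.1 itself names. A statistical analysis plan cannot repair this, since it can tabulate only what the forms collect. Later recovery would also be hard: section 7.2 leaves patients' details with the GP and deletes the mobile numbers after the 3-month analysis.

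**What to change.** Before enrolment starts:

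- **Section 6 and Annex 3.** Replace the CHD yes/no entry with a short tick list of the retained diagnosis: CHD, other cardiac, pulmonary embolism, other respiratory, neoplastic, chest wall, anxiety, other (specify). Keep the certainty scale. Add the main diagnosis to the hospitalisation field.
- **Annex 2.** Put the same list in the index form, or record the date of first diagnosis. Without one of these, diagnoses made after the index visit cannot be separated from those made at it.
- **Section 10.2.** Tabulate serious non-CHD diagnoses first made after the index visit by arm in (e) and (f), and by score group in (d).
- **Sections 3.4 and 8.2.** Include these diagnoses in the 3-month review. The 3-month entry comes from a telephone interview by research staff, so it should be marked as provisional and confirmed on the GP's 9-month form.

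The cost is a little more form-filling for GPs and research staff, some coding of free text, and one more row in the planned tables. The change concerns measurement only and leaves patient care untouched.
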